8. PARTICIPANT IDENTIFICATION

8.1. Study Participants

The sample size is 20 participants. In this instance, time and resource constraints make recruiting a larger sample challenging. While 20 participants may be smaller than the typical guideline of 30 suggested by (Billingham et al. 2013) it may still provide valuable insights.

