The final review at 12 weeks will involve a physical health check and questionnaires conducted at the baseline assessment and initial consultation. There will also be a follow up goal setting conversation to ascertain if the participant requires further

support. Information about delivery time, mode, application of intervention components, and retention/adherence rate will all be gathered by the Equality Health Advisor using either an electronic device or paper reporting form that will be transferred to an excel sheet.

The questionnaires are as follows.

- CASE REPORT FORM B
- PROMIS 10
- EQ-5D
- South Wales Social Wellbeing Scale

The physical tests are as follows:

- Blood Pressure and HR
- Height
- Weight
- BMI
- Waist Circumference

NB: If the participant feels uncomfortable with Equality Health Advisor visiting their home at any point, they will be offered an alternative of a telephone or video call. This will be recorded on the Equality Health home visit form.

Process Evaluation

Participants and Equality Health Advisor semi-structured interviews

As part of the final intervention process evaluation, a small cohort of participants (approximately 8-10) using a non-probability convenience sample as described by (Suen et al. 2014) will undertake a semi structured interview during the 12 week follow up visit. The semi structured interviews will be conducted by the researcher.

A set of standard questions will be asked to ascertain the following:

- The participant's experiences and perceptions of the Equality Health-CVD Intervention.
- The participant's acceptability of the intervention and study design.
- Challenges or opportunities of future research in reducing health inequalities in the community.

In addition, approximately 2-4 Equality Health Advisors will undertake a semi structured interview to explore their views of the EQUALITY HEALTH-CVD study using a similar thematic qualitative process as the participants.

In addition, the Equality Health Advisor will keep a reflective diary.

It should be noted that further interviews may be required if new data is still presenting itself after the final interview. This study aims to achieve theoretical saturation in that sampling will continue until eligible participant pool has been exhausted or interviews are not yielding new information.

Logic Model

Context	Intervention	Mechanisms of	Intervention outcomes
		impact	

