9.1. Recruitment

20 participants will be recruited over a 4-to-8-month period. The aim is to recruit a conservative 5 participants per month for a total of 4 months to reach a target recruitment of 20 participants. The following routes of recruitment will be used: Potential participants will be identified locally at sites across Aneurin Bevan University Health Board by cardiovascular disease, peripheral artery, and stroke specialists. Including emergency admission, in patient setting or consultant and nurse lead clinics.

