Follow up Completion	90-100% of participants complete the scheduled number of contact visits.	60-89% of participants complete the scheduled number of contact visits. Investigate barriers and enhance follow-up procedures.	< 75% of participants complete the scheduled number of contact visits Re-evaluate follow up strategy and consider protocol adjustments when considering future research.
Duration of visits	Average visit duration aligns with the planned schedule ± 10%	Average visit duration deviates from the planned schedule by 11-20%. Analyse time management and adjust visit plans if necessary.	Average visit duration deviates from the planned schedule by > 20%. Reassess visit structure and content.
Completion of Intervention Components	≥ 90% of participants complete all four components of the intervention.	75-89% completion rate. Identify and address barriers to the Labonte Model implementation	< 75% completion rate. Re-evaluate intervention design and implementation strategies.
Completion of Data Collection	≥ 95% of required data points collected	80-94% of required data points collected. Enhance data collection methods and follow-up.	80% of required data points collected. Implement corrective measures and consider protocol revisions.
Utilisation of Community and Public Service Asset	All planned community and public service assets are utilised as per individual goal plan	75-99% of planned assets are utilized. Identify reasons for underutilisation and adjust as necessary.	< 75% of planned assets are utilised. Conduct a thorough review and consider alternative assets or engagement strategies.
Participants' Acceptability and Perception			
Participant Satisfaction	≥ 80% of participants report	60-79% of participants report	< 60% of participants report

Perception of Effectiveness	high satisfaction with the intervention ≥ 80% of participants perceive the intervention as beneficial to their health and wellbeing.	high satisfaction. Investigate concerns and enhance the intervention based on feedback. 60-79% of participants perceive the intervention as beneficial. Address specific areas of concern to improve perceived effectiveness.	high satisfaction. Conduct a thorough review and consider major modifications to the intervention < 60% of participants perceive the intervention as beneficial. Re- evaluate the intervention's approach and content.
	Deliverers' Acceptal	oility and Perceived	Impact

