Equality Health Advisor Satisfaction	All Equality Health Advisors report high satisfaction with the implementation process. Use of Equality Advisor Handbook	Half of the Equality Health Advisors report high satisfaction. Identify and address concerns to enhance deliverer experience. Use of Equality Advisor Handbook	Equality Health Advisors do not report high satisfaction. Conduct a detailed review and consider significant modifications to the Equality Advisor Handbook and delivery process.
Identification of Barriers and Facilitators	Comprehensive identification of key barriers and facilitators, with actionable insights.	Partial identification with some actionable insights. Further investigation needed to fully understand and address issues.	Inadequate identification of barriers and facilitators. Implement a focused review and action plan to gather necessary insights.
Perceived Impact	All Equality Health Advisors perceive the intervention as having a positive impact on participants.	Half of the Equality Health Advisors perceive a positive impact. Explore specific areas for improvement.	Equality Health Advisors do not perceive a positive impact. Reassess and potentially redesign aspects of the intervention

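### Follow-up completion from 60% to just under 75% is both amber and red in the progression table, and no rule says which light prevails

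*Protocol*

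**What the plan says.** Section 12.1 of the Protocol sets out progression criteria as a table of green, amber and red lights.

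- **Follow-up completion.** Green is "90-100% of participants complete the scheduled number of contact visits", amber is "60-89% of participants complete the scheduled number of contact visits" and red is "< 75% of participants complete the scheduled number of contact visits". The row appears twice with the same bands, once under recruitment and attrition and once under feasibility of implementation.
- **Data completion.** Green is 95% or more and amber is 80-94%. The red cell reads "80% of required data points collected. Implement corrective measures and consider protocol revisions", with no inequality sign.
- **Adviser satisfaction and adviser perceived impact.** Green needs all advisers. Amber for satisfaction is "Half of the Equality Health Advisors report high satisfaction", and the perceived-impact row follows the same pattern. Red is worded as the advisers not reporting satisfaction or not perceiving a benefit.

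On numbers, section 8.1 states "The sample size is 20 participants", and section 9 (Process Evaluation) expects that "approximately 2-4 Equality Health Advisors will undertake a semi structured interview".

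**The concern.** A traffic-light table is useful only if each possible result maps to one light before the data are seen. Analysis is otherwise descriptive (section 1.1), so this table is the study's pre-set basis for judging feasibility, and follow-up completion bears on the primary feasibility objective. Where one result carries two lights, the team must choose the label after seeing the result. The labels lead to different actions: amber asks for barriers to be investigated and procedures strengthened, while red asks for the strategy to be re-evaluated and protocol changes considered.

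The table itself fixes these cut-offs and conflicts with itself, so this is not detail left to a later analysis plan.

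**Working it through.** **Inputs.** The planned n is 20 (section 8.1). Section 9.1 gives the basis: "The aim is to recruit a conservative 5 participants per month for a total of 4 months to reach a target recruitment of 20 participants", and 5 × 4 = 20 reproduces it. The bands are those printed in section 12.1. The number of advisers is about 2 to 4 (section 9).

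**Step 1: follow-up completion, all counts from 0 to 20.** The percentage is 100 × k / 20.

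| Completers k | Percentage | Lights as printed |
|---|---|---|
| 0-11 | 0-55% | red |
| 12 | 60% | amber and red |
| 13 | 65% | amber and red |
| 14 | 70% | amber and red |
| 15-17 | 75-85% | amber |
| 18-20 | 90-100% | green |

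Three of the 21 possible counts have two lights; every other count has one. The overlap in percentage terms (60% to below 75%) does not depend on the denominator.

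**Step 2: chance of landing in the overlap.** P(12 ≤ X ≤ 14) for X ~ Binomial(20, p) is the sum over k = 12, 13, 14 of C(20,k) p^k (1−p)^(20−k). The protocol states no expected completion rate, so p is an assumption and a range is shown. At p = 0.65 the three terms are 0.161 + 0.184 + 0.171 = 0.517 (from unrounded terms).

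| Assumed true completion | P(12, 13 or 14 of 20) |
|---|---|
| 50% | 0.231 |
| 60% | 0.470 |
| 65% | 0.517 |
| 70% | 0.470 |
| 75% | 0.342 |
| 80% | 0.186 |
| 85% | 0.066 |
| 90% | 0.011 |

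**Step 3: is the zone reachable under the plan's own terms?** Withdrawals are not replaced (section 9.4), and the attrition row shows green at 25% drop-out. If 5 of 20 leave and completion is counted over all recruited, at most 15 (75%) can complete. One further participant missing one visit gives 14/20 = 70%, which is in the overlap.

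**Step 4: comparison row.** The intervention-components row uses green from 90%, amber 75-89% and red below 75%. With n = 20, each count then gets exactly one light.

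**Step 5: data completion.** Read literally, exactly 80% is amber and red, and anything lower has no light. If red is read as below 80%, both problems vanish.

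**Step 6: adviser rows,** reading red as none of the advisers.

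| Advisers | Results with a light | Results without a light |
|---|---|---|
| 2 | 0/2, 1/2, 2/2 | none |
| 3 | 0/3, 3/3 | 1/3, 2/3 |
| 4 | 0/4, 2/4, 4/4 | 1/4, 3/4 |

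With three advisers, amber cannot be reached.

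**The case against.** Several limits on this point are fair and stand.

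- **The actions are advisory.** Neither the amber nor the red follow-up cell is a stop/go rule; only the attrition row mentions proceeding to an RCT. A reader might infer that the overlap would change the decision to progress, but the documents do not show that. What is undetermined is the light reported and the action attached to it.
- **The repeated row.** A reader might infer that one result is counted twice. The protocol has no rule that adds or weighs lights across rows, so the repetition is only redundant.
- **The 80% cell.** A reader might infer that poor data completion was left ungraded. The corrective action in that cell makes below 80% the natural reading, and a sign could have been lost in typing or in reading the PDF. However, the sign survives in neighbouring red cells, so the wording is worth confirming.
- **The adviser rows.** A reader might infer that three advisers cannot be graded at all. Unanimous results can be, and with two advisers every result can. These rows serve a secondary objective.
- **The probabilities.** They depend on assumed completion rates and are small if completion is 85% or better.

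None of this removes the follow-up overlap. Both bands are fully legible, and nothing in the protocol resolves 60% to just under 75%.

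**Conclusion.** The follow-up completion row is wrong as written: 12, 13 or 14 completers out of 20 are both amber and red. The overlap itself needs no assumption beyond the printed bands; the counts use the planned n of 20. How likely it is to matter does rest on an assumption. The chance is roughly one in three to one in two if true completion is 60-75%, about one in five at 80%, and slight at 90%.

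The data-completion cell is a probable missing sign to be confirmed. The adviser rows have a real but narrow gap, confined to split views of 1/3, 2/3, 1/4 and 3/4. The documents do not support saying that these rows cannot be scored in general; they fail only for the results listed.

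**What to change.** Amend the table before any outcome data are seen.

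1. **Follow-up completion.** Make the bands contiguous and list the row once. The documents support two options: (a) green 90% or more, amber 75% to below 90%, red below 75%, which matches the components row; or (b) green 90% or more, amber 60% to below 90%, red below 60%, which keeps the printed start of amber and matches the red cut-off in the participant satisfaction and perception rows. The sponsor must choose.
2. **Data completion.** Confirm that red means below 80%.
3. **Adviser rows.** Define amber so that every split result gets one light, for example amber for at least half but not all, and red for fewer than half.

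The cost is a table-wording amendment handled under section 9.5, with no change to visits, assessments or sample size. The choice in item 1 is not neutral: it decides whether a result from 60% to just under 75% is reported as amber or red. Likewise, the example in item 3 would make 1/3 and 1/4 red.

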13. DATA MANAGEMENT

13.1. Access to Data

All participant identification and referral procedures as well as procedures for data storage, processing and management will comply with Cardiff University policies. Direct access will be granted to authorised representatives from the sponsor and host institution for monitoring and/or audit of the study to ensure compliance with the relevant data protection legislation.

The study may be subject to inspection and audit by Cardiff University under their remit as sponsor and other regulatory bodies to ensure adherence to GCP and the UK Policy Framework for Health and Social Care Research 2017.

Direct access will be granted to authorised representatives from the sponsor and host institution for monitoring and/or audit of the study to ensure compliance with the relevant data protection legislation.

13.2. Data Recording and Record Keeping

The researcher and delegated staff will be GDPR compliant, and data collected will be stored on a secure NHS server that only the researcher and delegated research staff are able to access for the duration of the study. The data will be collected using a ABUHB laptop using Microsoft word and an excel database. If a paper based CRF or Equality Health form is utilised a copy of the completed form will be scanned and saved in the Equality Health site file in a Research and Development SharePoint folder.

Equality Health-CVD data validity and data quality will be monitored by a member of the ABUHB Office of Population Health team named on the delegation log.

Anonymisation of data will be conducted throughout study implementation and during the analysis and will include removing direct identifiers between the screening and recruitment log and the Equality Health database. In addition to generalising specific demographics and contextual details. Intervention outcome data will remain anonymised to the public, with only the researcher and delegated staff having access to identifiable personal data.

All information collected during the study will be kept strictly confidential. Personal data will be kept on file for the minimum amount of time as necessary, with the exception of study consent forms which will be retained for a further 15 years in accordance with Cardiff University data retention requirements.

The study master trial file will be transferred to Cardiff University secure servers at the end of the student thesis submission for long term storage.

13.3. Participant Confidentiality and Data Protection

All investigators and study site staff must comply with the requirements of the General Data Protection Regulation (GDPR) and Data Protection Act 2018 with regards to the collection, storage, processing, and disclosure of personal information and will uphold the Act's core principles.

All data will be anonymised, and recordings of transcribed data will be kept no longer than necessary. Research data will be kept securely and separately from any personal data collected as part of the study.

Electronic Data –The CI will maintain separate databases with and without participant identifiable data (PID). All data stored electronically will be stored on local NHS IT assets, and access to the data will be restricted to only those delegated to access the data via the delegation log and the CI.

Hard Copy Data – Where data exists in hard copy, the CI and delegated staff are responsible for ensuring safe and secure storage of either identifiable or non-identifiable data. The data will be kept with ABUHB research and development department until the end of the study.

At the end of the study, all data will be transferred to Cardiff University secure servers and locations for long term storage.

The CI and research team is responsible for the data entry, quality of the data and data analysis. The CI will act as the data custodian and data controller for this study.

13.4 Record Storage and Retention

The TMF and ISF containing essential documents will be kept for a minimum of 15 years after completion of study in line with Cardiff University data retention requirements. Documents (paper and electronic) will be retained in a secure location during and after the study has finished. A label stating the required retention time should be placed on the inside front cover of the medical records for study participants. Each PI at any participating site will archive the essential documents generated at the site for the agreed archiving period in accordance with the signed Site agreement and Cardiff University data retention policies.

Essential documents pertaining to the study shall not be destroyed without permission from the sponsor.

14. QUALITY ASSURANCE PROCEDURES

The study may be subject to inspection and audit by Cardiff University under their remit as sponsor and other regulatory bodies to ensure adherence to GCP and the UK Policy Framework for Health and Social Care Research 2017.

15. ETHICAL AND REGULATORY CONSIDERATIONS

The study will be conducted in compliance with the principles of the Declaration of Helsinki (2013) and the principles of GCP and in accordance with all applicable regulatory guidance, including but not limited to the UK Policy Framework for Health and Social Care 2017.

This protocol and related documents (and any subsequent amendments) will be submitted for review to the relevant parties (HRA/HCRW and REC). Annual progress reports and a final report at the conclusion of the study will be submitted to the relevant parties within the timelines defined if required.

15.1. Review and Approvals

15.1.1. Ethical Approval and HRA/HCRW approval

- Before the start of the study, approval will be sought from HRA/HCRW and REC for the protocol, informed consent forms and other relevant documents e.g. advertisements and GP information letters
- Amendments that require review by HRA/HCRW and REC will not be implemented until approval is granted. The CI (or delegate) should submit any amendments through the IRAS Identity Gateway. This will automatically submit the amendment to both REC and HRA /HCRW.
- The chief investigator (or delegate) also needs to notify the R&D offices and local research teams the amendment(s). The R&D Office(s) will have 35 days from receipt of the amendment to confirm capacity and capability.
- All correspondence with the REC will be retained in the TSF/ISF
- It is the Chief Investigator's responsibility to produce the annual reports as required.
- The Chief Investigator will notify the REC of the end of the study
- If the study is ended prematurely, the Chief Investigator will notify the REC, including the reasons for the premature termination
- Within one year after the end of the study, the Chief Investigator will submit a final report with the results, including any publications/abstracts, to the REC

15.1.2. Peer Review

This study has been funded by the Stroke Implementation Group. The protocol has been peer reviewed by Educational Supervisors [name] and [name]

15.1.3. Governance Review

The study will be assessed for governance and legal compliance by HCRW. Once all checks are satisfied HCRW will issue HRA/HCRW approval. The study should not

commence at any site until local confirmation of capacity and capability is also received via email by the CI/ PI.

15.2. Reporting

The CI shall submit once a year throughout the study or on request, a progress report to the REC and sponsor (as required). In addition, an end of study notification and final report will be submitted to the relevant parties.

15.3. Expenses and Benefits and PPI consultation

PPI consultation

The acceptability of the study design has been informed through extensive PPI. The protocol was drafted by the researcher then subsequently informed following three focus groups and several one-to-one interviews.

An online focus group was held on Tuesday 6th February 2024 10am – 11.30am. Health Professionals and Professionals from Public Services Board (PBS) organisations attended and helped inform the protocol.

The recruitment of the public, patient involvement group (those with lived experience) derived from the ABUHB Community Neurological Rehabilitation Service, with the ABUHB Head of Community Neurological Conditions Service contacting two established Gwent patient support groups.

The Stroke reference group received an email on 31st January 2024, inviting them to participate in an online focus group via a "teams" online platform on 13th February 2024, starting at 11 a.m. The Community Neurological Rehabilitation team set up another in-person focus group on 13th February 2024, at Cwmbran Stadium at 3:30 p.m.

In accordance with National Institute for Health Care Research recommendations all participants received a £25 expenses voucher for their contribution.

A focus group and one to one interview evaluation report prepared by the researcher was sent out to all focus group workshop members on 26th March 2024 and is available to the REC upon request.

Further PPI consultation was sought between 6th-18th May 2024. In addition, 1/2 PPI members will continue to support the study by attending and contributing to the SOG during the implementation phase. The PPI representatives will be paid a £25 expenses voucher for contributing to meetings, reviewing study materials, or contributing to study dissemination.

Research Participants Expenses

The aim of the study is to ascertain the feasibility of the Equality Health intervention. For this reason, participants recruited into the study will not be reimbursed for participation. However, if during the consent phase participants are asked to attend an additional consent appointment outside of standard of care, the participants will be offered reasonable travel expenses.

16.INDEMNITY AND FINANCE

